#### NOTE: Baseline definitions:

- For PD assessments, there are 5 pre-treatment baseline samples (-168, -156, -24, -12, and 0h) to be collected. The average value will be used for Baseline.
- For PK, antibody, and laboratory assessments, Baseline is Day 1 pre-dose sample.
- For Safety assessments, the last assessment prior to first dose will be used for Baseline
- 1. The Safety Follow-Up telephone call will occur 90 days after the last dose of study drug. Males and females of child-bearing potential will be followed up for birth control and pregnancy information. Any reported pregnancies in female patients or female partners of male patients will be followed until the outcome of the pregnancy is known. Refer to Section 9.4.1.10 for further details.
- 2. The Week 1, Day 1 single dose must be administered on a Monday, and the multiple dosing in Week 3 through Week 9 must be administered on Mondays, Wednesdays, and Fridays.

- 3. To facilitate scheduling of required study assessments at each visit, the study visit may be shortened or prolonged, as necessary, as long as the specified order of assessments and/or availability of results pertaining to laboratory work (including PK and pregnancy and asfotase alfa anti-drug antibody testing) and vital signs are adhered to.
- 4. The patient's Week 13 visit will be considered their End of Study visit. If a patient who withdraws or discontinues from the study prior to Week 13, a separate End of Study visit will be scheduled.
- 5. If the time period between the initial Screening and the re-Screening is >12 weeks, all Screening procedures must be repeated.
- 6. Demographics will be collected as permitted by region and may include date and region of birth, age, sex, ethnicity, race, and whether the patient is of Japanese descent.
- 7. Medical history includes general medical history and HPP-specific medical history, including detail of pediatric-onset. Details of loss of adult teeth will be included as part of medical history.
- 8. PHPP gene mutation analysis will be performed during Screening or the Rn-In Period if results are not available in the medical records.
- 9. Concomitant medications and therapies must be collected from 30 days prior to study entry up until the final study visit. All available historical use of certain medications (ie, related to HPP, growth, etc.) will be captured.
- 10. Physical examination will include assessment of general appearance; skin; head, ear, eye, nose, and throat; neck; lymph nodes; chest; heart; abdominal cavity; limbs; central nervous system; musculoskeletal. At Screening and Baseline visits, a complete physical examination will be performed. Thereafter, limited physical examinations (based on the patient's signs/symptoms) may be performed. All physical examinations (complete and limited) will include weight (using a calibrated scale) and examination of asfotase alfa injection sites for potential reaction(s). The Screening and Baseline physical examination will include height (using a wall-mounted standiometer).
- 11. Vital signs include blood pressure, heart rate, respiratory rate, and temperature. On dosing days in the clinic or under medical supervision at home, vital signs will be taken within 10 minutes before study drug injection.
- 12. Required PIn-Clinic or inpatient study visits will occur during Screening, the Run-In Period (Week -1), Week 1, Week 9, and Week 13. At the discretion of the Investigator, Week 2 through Week 8 and Week 10 through Week 12 visits may be conducted in the clinic or at home by a home healthcare provider.
- 13. Urine and serum pregnancy testing is required for women of childbearing potential only. Serum pregnancy testing is required at Screening and EOS visits; pregnancy testing at Run-In Period, Day 1 visit, and Week 9 visit can be either urine or serum testing at the discretion of the Investigator. Results of pregnancy testing must be negative prior to study drug administration (when applicable).
- 14. Study drug will be administered in the clinic for the first dose and all other doses that occur during study visits. All other study drug administration will occur at home under the supervision of home healthcare.
- 15. All patients are required to fast for 8 hours prior to laboratory testing (water all ad libitum). All urine and blood samples for laboratory assessments must be collected prior to study drug administration. Single exception is blood sample collection for analysis of PK parameters at required post-dose timepoints. For all patients, fasting samples should be collected at the beginning of the visit day, before any other study-related procedures are performed.
- 16. A full ophthalmology examination will be performed at scheduled visits. The examination will assess for papilledema and signs of ectopic calcification, and will include assessments of visual acuity; adnexa; and slit-lamp biomicroscopy with examination of anterior chamber, lens, conjunctiva, cornea, and fundus. The ophthalmology examination should be performed by a qualified ophthalmologist. Sites will be provided ophthalmologic worksheets required to complete the full exam. Ophthalmology exams may be performed by a qualified optometrist (i.e., Doctor of Optometry, O.D.) as long as the optometrist works under the supervision of an ophthalmologist.
- 17. As fotase alfa anti-drug antibody testing and PK/PD analyses must be performed on samples obtained at the same time (ie, pre-dose samples from the same study visit).
- 18. Refer to Table 3 for timing of PK/PD and asfotase alfa anti-drug antibody assessments.
- 19. Serum sample for tryptase will be collected pre-dose on Day 1. Samples will be drawn only if the patient has no active allergies at the time, and will only be analyzed if the patient experiences a subsequent IAR. For acute or severe IARs (eg, with signs/symptoms of hypersensitivity, irrespective of the time from administration of study drug to onset), additional blood and urine samples must be collected to assess the reaction as described in Section 9.4.2.1.1 and detailed in the SOM.
- 20. For systemic hypersensitivity reactions, additional blood and urine samples must be collected to assess the reaction. Refer to Section 9.5 for details of sample collection.
- 21. Refer to SOM for additional information.

Table 3: Schedule of Events – Pharmacokinetic, Pharmacodynamic, and Immunogenicity Assessments

	West	Compline Times	Dosing 	PK, PPi and	ADA
D I D ' 1	Week	Sampling Times	8	PLP 1 DL D	ADA
Run-In Period	Week -1	Day -7: -168h, -156h pre-dose	NA	PPi and PLP	NA
	*** 1 1	Day -1: -24h, -12h pre-dose	B1 ( ! 1 1 )	only	
Single Dose	Week 1	Day 1: pre-dose; post-dose 6h, 12h	D1 (single-dose)	All	Day 1: pre-dose
No Dosing	Week 1	Day 2: post-D1 dose 24h, 32h, 36h Day 3: post-D1 dose 48h, 56h, 60h Day 4: post-D1 dose 72h Day 5: post-D1 dose 96h Day 6: post-D1 dose 120h Day 7: post-D1 dose 144h	None	All	
No Dosing	Week 2	Day 8: post-D1 dose 168h	None	All	Day 8: post-D1 dose 168h
No Dosing	WEEK Z	Day 11: post-D1 dose 240h	None	All	Day 8. post-D1 dose 10811
Weekly Dosing	Week 3	Day 15: pre-dose, post-dose 6h	D15, D17, D19	All	Day 15: pre-dose
(3 times per	Week 4	Day 22: pre-dose, post-dose 6h	D22, D24, D26	All	Day 22: pre-dose
week)	Week 5	Day 29: pre-dose (trough), post-dose 6h	D29, D31, D33	All	Day 29: pre-dose
	Week 6	None	D36, D38, D40	None	None
	Week 7	Day 43: pre-dose (trough), post-dose 6h	D43, D45, D47	All	Day 43: pre-dose
	Week 8	Day 50: pre-dose (trough), post-dose 6h	D50, D52, D54	All	Day 50: pre-dose
	Week 9	Day 57: pre-dose Day 61: pre-dose (trough), post-dose 6h, 12h Day 62:post-D61 dose 24h, 32h, 36h, Day 63:post-D61 dose 48h, 56h, 60h	D57, D59, D61	All	Day 61: pre-dose
No Dosing	Week 10	Day 64: post-D61 dose 72h Day 65: post-D61 dose 96h Day 66: post-D61 dose 120h Day 67: post-D61 dose 144h Day 68: post-D61 dose 168h	None	All	Day 68: post-D61 dose 168h
	Week 11	Day 71: post-D61 dose 240h Day 75: post-D61 dose 336h	None	All	Day 75: post-D61 dose 336h
	Week 12	Day 80: post-D61 dose 456h	None	All	Day 80: post-D61 dose 456h
	Week 13	Day 87: post-D61 dose 624h	None	All	Day 87: post-D61 dose 624h

Abbreviations: ADA = anti-drug antibodies; PK = pharmacokinetics; PLP = pyridoxal 5'-phosphate; PPi = inorganic pyrophosphate; SOM = Study Operations Manual; D = day; h = hour

NOTE: Trough is defined as pre-dose concentration (ie, concentration data-point collected just prior to the next dose).

#### NOTE: Baseline definitions:

• For PD assessments, there are 5 pre-treatment baseline samples (-168, -156, -24, -12, and 0h) to be collected. The average value will be used for Baseline.

- For PK and immunogenicity assessments, Baseline is Day 1 pre-dose sample.
- Timepoints for pre-dose PK sample collection have a window of -15 minutes and for post-dose PK sample collection have a window of ±15 minutes. For additional instructions, please refer to the SOM.
- 2 The Week 1, Day 1 single dose must be administered on a Monday, and the multiple dosing in Week 3 through Week 9 must be administered on Mondays, Wednesdays, and Fridays.

#### 7. STUDY POPULATION

#### 7.1. Inclusion Criteria

Patients must meet all of the following inclusion criteria to be eligible for participation in this study:

- 1. Patients or their legal representative(s) must provide written informed consent prior to undergoing any study-related procedures
- 2. Patient has pediatric-onset HPP, defined as onset of first sign(s)/symptom(s) of HPP prior to 18 years of age
- 3. Patients must have a documented diagnosis of HPP as indicated by a documented history of HPP-related skeletal abnormalities and 1 or more of the following:
  - Documented TNSALP gene mutation(s) from a certified laboratory
  - Serum ALP level below the age-adjusted normal range AND plasma PLP above the upper limit of normal at Screening.

NOTE: Historical results from a certified laboratory for PLP may be used to determine patient eligibility. The criterion for plasma PLP is not applicable if the patient is receiving pyridoxine treatment.

- 4. Patients must have a plasma PPi level of ≥3.9 μM at Screening
- 5. Patients must be  $\geq$ 18 years of age at Screening
- 6. Sexually active male and female patients of childbearing potential must agree to use a highly effective method of birth control during the study and for 3 months following the last dose of study drug. Male patients must also not donate sperm during the Screening and treatment periods and for at least 3 months after the last dose of asfotase alfa. Highly effective contraceptive methods are as follows:
  - a. Combined (estrogen and progestogen containing) hormonal contraception associated with inhibition of ovulation:
    - Oral
    - Intravaginal
    - Transdermal
  - b. Progestogen-only hormonal contraception associated with inhibition of ovulation:
    - Oral
    - Injectable
    - Implantable
  - c. Intrauterine device
  - d. Intrauterine hormone-releasing system
  - e. Bilateral tubal occlusion

- f. Vasectomy with documented medical assessment of surgical success
- g. Condom and spermicide
- 7. Female patients of childbearing potential must have a negative pregnancy test at the time of enrollment
- 8. Female patients not of child-bearing potential due to surgical sterilization (at least 6 weeks after surgical bilateral oophorectomy with or without hysterectomy or at least 6 weeks after tubal ligation) confirmed by medical history, or menopause
  - a. Menopausal women include women with either
    - Spontaneous amenorrhea for at least 12 months, not induced by a medical condition such as anorexia nervosa and not taking medications during the amenorrhea that induced the amenorrhea (for example, oral contraceptives, hormones, gonadotropin releasing hormone, antiestrogens, selective estrogen receptor modulators, or chemotherapy), or
    - Spontaneous amenorrhea for 6 to 12 months and a follicle-stimulating hormone level >40 mIU/mL or estradiol level ≤110 pmol/L
- 9. Patients must be willing to comply with study procedures and the visit schedule

#### 7.2. Exclusion Criteria

Patients will be excluded from participation in this study if they meet any of the following exclusion criteria:

- 1. Investigational site personnel directly affiliated with this study and/or their immediate families. Immediate family is defined as a spouse, parent, child, or sibling, whether biological or legally adopted.
- 2. Employees of Alexion Pharmaceuticals
- 3. Currently enrolled in a clinical study involving another study drug or nonapproved use of a drug or device, or concurrently enrolled in any other type of medical research judged not to be scientifically or medically compatible with this study (excluding the HPP registry, in which concurrent enrollment is allowed).
- 4. Participated, within the last 30 days, in a clinical study involving a study drug (other than the study drug used in this study). If the previous study drug has a long half-life, 3 months or 5 half-lives (whichever is longer) should have passed.
- 5. Have completed or withdrawn from this study or any other study investigating as fotase alfa in the previous 3 years. This exclusion criterion does not apply to patients who are re-screened prior to randomization or patients enrolled in the HPP registry.
- 6. Women who are pregnant, planning to become pregnant, or breastfeeding
- 7. Serum 25-OH Vitamin D below 20 ng/mL at Screening (results from local laboratory may be used if within 4 weeks of Screening)
- 8. Screening serum creatinine or parathyroid hormone (PTH) levels 1.5 times the upper limit of normal

- 9. Medical condition, serious concurrent illness and/or injury, recent orthopedic surgery, or other extenuating circumstance that, in the opinion of the Investigator, may significantly interfere with study compliance or study endpoints, including all prescribed evaluations and follow-up activities
- 10. Prior treatment with bisphosphonates within 2 years of study entry for any length of time or for more than 2 consecutive years at any prior timepoint
- 11. Treatment with PTH, strontium, or sclerostin inhibitors within 6 months prior to the first dose of study drug
- 12. Unwilling or unable to comply with the use of a data collection device on which study patients will directly record data

#### 7.3. Discontinuations

#### 7.3.1. Discontinuation of Patients

The criteria for enrollment must be followed explicitly. If the investigational site identifies a patient who did not meet enrollment criteria and who was inadvertently enrolled, the Sponsor must be notified. If the Sponsor identifies a patient who did not meet enrollment criteria and who was inadvertently enrolled, the investigational site will be notified. A discussion must occur between the Sponsor's Medical Monitor and the Investigator to determine whether the patient may continue in the study, with or without study drug. Ineligible patients who are inadvertently enrolled may be maintained in the study and on study drug when the Sponsor's Medical Monitor agrees with the Investigator that it is medically appropriate for that patient. The patient may not continue in the study with or without study drug if the Sponsor's Medical Monitor does not agree with the Investigator's determination that it is medically appropriate for the patient to continue. The Investigator must obtain documented approval from the Sponsor's Medical Monitor to allow the inadvertently enrolled patient to continue in the study with or without study drug.

In addition, patients will be discontinued from the study drug and/or from the study in the following circumstances:

- Enrollment in any other clinical study involving a study drug or enrollment in any other type of medical research judged not to be scientifically or medically compatible with this study
- Investigator Decision
  - The Investigator decides that the patient should be discontinued from the study
  - If the patient, for any reason, requires treatment with another therapeutic agent that has been demonstrated to be effective for treatment of HPP, discontinuation from the study will occur prior to introduction of the new agent
- Patient Decision
  - The patient requests to be withdrawn from the study

#### • Sponsor Decision

 Alexion or designee stops the study or stops the patient's participation in the study for medical, safety, regulatory, or other reasons consistent with applicable laws, regulations, and Good Clinical Practice (GCP)

#### • Adverse Event

If the Investigator decides that the patient should be withdrawn because of a serious AE (SAE) or a clinically significant laboratory value, the study drug is to be discontinued and appropriate measures are to be taken. Alexion or designee is to be alerted immediately. Refer to Section 9.4.1.11.

Patients who discontinue the study drug and/or study early will have end-of-study procedures performed as shown in the Schedule of Events (Table 2).

All AEs ongoing at the time of withdrawal require 30 day follow-up. The Investigator will be asked to follow all SAEs that were ongoing at the time of withdrawal until resolution or until the patient is lost to follow-up.

#### 7.3.2. Discontinuation of Study Sites

Study site participation may be discontinued if Alexion or designee, the Investigator, or the institutional review board, independent ethics committee, or research ethics board (IRB/IEC/REB) of the study site judges it necessary for medical, safety, regulatory, or other reasons consistent with applicable laws, regulations, and GCP.

### 7.3.3. Discontinuation of Study

The study will be discontinued if Alexion or designee judges it necessary for medical, safety, regulatory, or other reasons consistent with applicable laws, regulations, and GCP.

#### **8.** TREATMENT

#### **8.1.** Treatments Administered

This study involves an evaluation of asfotase alfa administered by SC injection at doses of thrice-weekly 0.5 mg/kg (1.5 mg/kg/week), 2.0 mg/kg (6.0 mg/kg/week), and 3.0 mg/kg (9.0 mg/kg/week). Asfotase alfa should be administered only as a SC injection and should not be administered intravenously or intramuscularly. The maximum volume of medicinal product per injection should not exceed 1.0 mL. If more than 1.0 mL is required, multiple injections may be administered at the same time. Table 4 presents the treatment regimens.

**Table 4:** Treatment Regimens

Cohort	Regimen and Dose
Cohort 1	Asfotase alfa 0.5 mg/kg initial single dose; followed by multiple dosing starting after 2 weeks at
	0.5 mg/kg 3 times per week
Cohort 2	Asfotase alfa 2.0 mg/kg initial single dose; followed by multiple dosing starting after 2 weeks at
	2.0 mg/kg 3 times per week
Cohort 3	Asfotase alfa 3.0 mg/kg initial single dose; followed by multiple dosing starting after 2 weeks at
	3.0 mg/kg 3 times per week

The total amount of asfotase alfa administered may be adjusted at each study visit to account for changes in body weight.

The Investigator or designee is responsible for the following:

- Explaining the correct use of the study drug to the patient or legal representative
- Verifying that instructions are followed properly
- Maintaining accurate records of study drug dispensing and collection
- Returning all unused study drug to the Sponsor or designee at the end of the study

# 8.2. Clinical Study Materials and Supplies

Asfotase alfa is a fusion protein made from the soluble catalytic domain of human TNSALP, the human IgG1 Fc domain for purification, and a deca-aspartate peptide used as a bone targeting domain. It is derived from Chinese Hamster Ovary cells and is supplied as a clear, colorless, sterile solution for injection in single use glass vials.

Table 5 summarizes the concentrations and extractable amounts of study drug that will be used for the study.

 Table 5:
 Summary of Vial Concentrations and Extractable Volumes

Concentration	Extractable	Extractable		
	Volume (mL)	Product (mg)		
100 mg/mL	0.8	80		

At a minimum, study drug will be labeled with:

- The protocol number
- Lot number/expiry date

- Sponsor name and address
- Instructions for use and storage

Study drug will be labeled according to the country's regulatory requirements.

Study drug must be refrigerated between 2°C and 8°C in a secure area with limited access immediately upon receipt and inventory at the investigational site. To ensure the integrity of the study drug, storage temperature at the investigational site must be monitored on a daily basis and appropriately documented throughout the study conduct. Study drug administered for home use by patients should be stored refrigerated at 2 C to 8°C.

The following guidelines must be adhered to where study drug handling is concerned:

- The Investigator must only supply study drug to patients enrolled in the clinical study
- The Investigator must ensure study drug is stored under controlled storage conditions, accessible only to those authorized by the Investigator to dispense the study drug
- The Investigator must ensure that study drug accountability is maintained on an ongoing basis during the study
- At the conclusion or termination of the study, after final accountability for study drug
  inventory has been performed, the Investigator must ensure unused study drug supplies at
  the investigational site are returned to Alexion or designee in accordance with Sponsor
  instructions or destroyed if the site has appropriate facilities and written procedures to
  dispose of study drug

Additional information on study drug accountability, handling, and disposal requirements can be found in the Pharmacy Manual.

**Note:** In some cases, sites may be permitted to destroy the study drug if, during the investigational site selection, the study monitor has verified and documented that the site has appropriate facilities and written procedures to dispose of study drug. The material must first be counted, reconciled, and approved for destruction by the Sponsor or designee.

# **8.3.** Method of Assignment to Treatment

Patients who meet all criteria for enrollment will be randomized to a cohort during Run-In Period (Week -1). Assignment to cohorts will be determined by a computer-generated random sequence using an interactive voice- or web- response system (IXRS). Enough vials for the calculated doses between visits will be dispensed to study patients at each visit.

Approximately 27 adult patients who meet eligibility criteria for study participation will be randomized to in a 1:1:1 ratio to 1 of the following 3 cohorts:

- Cohort 1: 0.5 mg/kg initial single dose; followed by multiple dosing starting after 2 weeks at 0.5 mg/kg 3 times per week
- Cohort 2: 2.0 mg/kg initial single dose; followed by multiple dosing starting after 2 weeks at 2.0 mg/kg 3 times per week
- Cohort 3: 3.0 mg/kg initial single dose; followed by multiple dosing starting after 2 weeks at 3.0 mg/kg 3 times per week dosing

Randomization will be stratified by gender to ensure a similar distribution of gender in each cohort.

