# 8.5. Selection and Timing of Doses

Patients will be randomly assigned by IXRS to 1 of the 3 cohorts (Table 4). Weekly doses of asfotase alfa will be administered 3 days per week as detailed in Section 8.1.

The number of vials used to prepare injections will be determined based on the patient's weight at that visit. The first dose of asfotase alfa will be prepared and administered at the investigational site on the Week 1, Day 1 study visit. Asfotase alfa will also be prepared and administered at the investigational site on dosing days that occur during all required study visits. The Investigator, patient, or designee may prepare and administer injections at study visits. For injections between study visits, asfotase alfa may be prepared and administered by the patient or designee at home under the supervision of home healthcare.

If a patient experiences an acute or severe IAR at home (eg, with signs/symptoms of hypersensitivity, irrespective of the time from administration of study drug to onset), the patient or legal representative(s) should call the site as soon as possible to discuss with the Investigator the need for medical evaluation in the medical office/hospital. Collection of blood samples for analyses outlined in Section 9.5 may be required upon recommendation of the Investigator and availability of these tests at the local laboratory.

Throughout the study, injection sites should be rotated among 8 different body areas (both thighs and buttocks, both sides of the abdomen, and both upper arms) and carefully monitored for sign(s) of potential reaction(s). Note that any injection sites with unresolved injection site reactions (ISRs) should not be used for injections again until the reaction subsides.

Full instructions for data collection using the electronic diary are included in the SOM.

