# 8.6. Blinding and Unblinding

This is an open-label study.

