## 11.1. Analysis Populations

#### 11.1.1. Full Analysis Set

The Full Analysis Set (FAS) consists of all patients who are randomized to treatment and received at least 1 dose of study drug and have at least 1 pre-treatment and 1 on-treatment PPi result. All analyses of PD/efficacy will be performed based on the FAS. Patients will be included in the analyses according to the treatment cohort to which they were randomized, irrespective of the treatment they actually received. The efficacy analyses based upon the FAS will be considered the primary analysis of efficacy.

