# 6. DATA SETS ANALYZED (STUDY POPULATIONS)

# 6.1. Full Analysis (FA) Set

Patients who have been randomized and received at least one dose of study drug that have at least one pre-treatment and one on-treatment PPi result will be included in the FA set. Patients will be included in the analyses according to the treatment cohort to which they were randomized, irrespective of the treatment they actually received.

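### Open-label cohorts are assigned up to a week before the first dose, and the primary analysis set leaves out anyone who withdraws in between

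*Protocol*

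**What the plan says.** Protocol Section 8.3 sets the time of allocation: "Patients who meet all criteria for enrollment will be randomized to a cohort during Run-In Period (Week -1". Table 2 shows that week as Day -7 to Day -1, and no text fixes a day within it. Section 8.5 sets the first dose: "The first dose of asfotase alfa will be prepared and administered at the investigational site on the Week 1, Day 1 study visit". Section 8.6 says only "This is an open-label study", and neither document withholds the cohort from patient or site until Day 1. Section 7.3.1 allows a patient to withdraw on request.

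Protocol Section 11.1.1 defines the set for the primary efficacy analysis. It "consists of all patients who are randomized to treatment and received at least 1 dose of study drug" and also have at least one PPi result before treatment and one on treatment. SAP Section 6.1 keeps the restriction: "Patients who have been randomized and received at least one dose of study drug", with the same PPi requirement. Under Protocol Section 11.5.3 and SAP Section 7.1.1, disposition is reported by cohort for all randomised patients; the SAP adds reasons for discontinuation.

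**The concern.** Leaving undosed patients out of the analysis is harmless when nobody's decision to withdraw before dosing can depend on the cohort. That condition is not secured here, because the cohort can be known for up to a week before the first injection. There is also a conceivable motive: the lowest cohort receives 1.5 mg/kg/week, a quarter of the 6.0 mg/kg/week that the protocol describes as effective in children (1.5 / 6.0 = 0.25). That cohort is the reference for both primary comparisons, and both must reach significance for the primary endpoint to be met.

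If withdrawal depends on the cohort and is also related to how a patient's PPi would have responded, the patients left in the cohorts are no longer comparable by randomisation. A patient lost before dosing has no PPi value after treatment, so this cannot be repaired at the analysis stage.

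**Working it through.** **1. Length of the window.** The Run-In Period is Day -7 to Day -1. Its first PD sample is at -168 h (168 / 24 = 7 days before the dose) and the Day -1 sample is at -24 h. Allocation therefore comes about 1 to 7 days before the first dose, depending on the day used.

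**2. Does any planned PPi analysis reach an undosed patient?**
- Primary mixed model (SAP 7.2.1): FA Set, missing values handled under a missing-at-random assumption (SAP 7.2.1.1). No.
- Exact Wilcoxon test with LOCF and with observed cases (SAP 7.2.1): FA Set. No.
- ANCOVA with LOCF and with observed cases (SAP 7.2.1.5): FA Set. No.
- Per Protocol analyses (SAP 6.2, 7.2.1): a subset of the FA Set. No.

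Only the disposition summary shows such a patient.

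**3. The plan's own power figures.** Inputs from Protocol Section 11.5.8: SD 1.5 µM and a two-sided two-sample t-test at 0.05. Power comes from the noncentral t distribution with noncentrality (difference / SD) × √(n/2).
- n = 9, difference 2.3 µM: (2.3 / 1.5) × √4.5 = 3.25, power 86.3%. The plan says above 80%: reproduced.
- n = 6, difference 3.2 µM: (3.2 / 1.5) × √3 = 3.70, power 91.4%. The plan says above 90%: reproduced.

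Both are figures for a single comparison.

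**4. Loss unrelated to response.** With 27 randomised 1:1:1, a cohort has 27 / 3 = 9 patients. One loss is 1/9 = 11% and two are 2/9 = 22%. If only the 0.5 mg/kg cohort loses patients, power for 2.3 µM in one comparison is:

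| Patients left in the 0.5 mg/kg cohort | Power |
|---|---|
| 9 | 86.3% |
| 8 | 83.9% |
| 7 | 80.8% |
| 6 | 76.7% |

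**5. Loss related to response (assumed).** The documents give neither a refusal rate nor a link between refusal and response, so both are varied. The simulation has no true difference, 9 patients per cohort, SD 1.5 µM, an unadjusted t-test and 40,000 replicates. The patients lost from the 0.5 mg/kg cohort are those with the most extreme score on a variable that has correlation rho with their later PPi change. The direction is chosen so that would-be large falls are lost and the higher dose looks better. Each cell gives the size of the spurious mean difference and the type I error of one comparison:

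| rho | 1 lost | 2 lost | 3 lost |
|---|---|---|---|
| 0 | about 0 µM, 5% | about 0 µM, 5% | about 0 µM, 5% |
| 0.3 | 0.08 µM, 5.1% | 0.15 µM, 5.4% | 0.22 µM, 5.9% |
| 0.5 | 0.15 µM, 5.7% | 0.26 µM, 6.4% | 0.37 µM, 7.3% |
| 1 (worst case) | 0.28 µM, 7.7% | 0.53 µM, 11.9% | 0.75 µM, 17.0% |

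The simulation standard error near 5% is √(0.05 × 0.95 / 40,000) = 0.1 percentage point, so 5.1% cannot be told from 5%. For one or two losses at rho 0.3 to 0.5, the spurious difference is at most 0.26 µM, or 0.26 / 2.3 = 11% of the design difference.

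**The case against.** The strongest reply is that the risk is hypothetical and small. Assignment is central through the IXRS, every cohort receives active drug, PPi is a laboratory measurement, and nothing in the documents suggests that patients will refuse. With two unselective losses, power is still above the stated 80%. Type I errors of 12% or more need refusal to be perfectly correlated with later PPi change. All of this stands and limits the size of the point.

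A second reply is that allocation on Day 1 does not stop cohort-driven loss. A patient can still refuse on Day 1, or take one dose and leave. The primary model in SAP Section 7.2.1 uses troughs from Day 22 to Day 61 only, so a patient who leaves before Day 22 is in the FA Set but contributes no response to the model. This also stands: the change narrows the window and no more.

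Three stronger readings are tempting but not supported:
- *Allocation may precede confirmed eligibility.* Table 2 footnote 8 says that "gene mutation analysis will be performed during Screening or the Rn-In Period", but only when no result is on record. Sections 6.1 and 8.3 allow only patients who already meet the criteria to be randomised, and inclusion criterion 3 offers ALP with PLP as an alternative to the gene result.
- *Knowing the cohort could distort the PPi baseline.* For PD, "there are 5 pre-treatment baseline samples (-168, -156, -24, -12, and 0h) to be collected", and the last sample does follow allocation. The documents offer no mechanism by which knowing the cohort would change a PPi assay.
- *Supply cannot require early allocation.* Table 5 does list a single vial presentation, but supply detail is left to the Pharmacy Manual, and drug lot assignment is a covariate in the SAP models. Whether lots must be assigned or shipped before Day 1 cannot be judged from these documents.

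**Conclusion.** The point holds as a modest, conditional weakness. In this open-label trial the cohort can be known up to a week before dosing, both documents remove undosed patients from the primary set, and no planned PPi analysis covers them. If nobody is lost before dosing, there is no effect. If patients are lost for reasons unrelated to response, the cost is power: 86.3% falls to 83.9% with one loss in the 0.5 mg/kg cohort and to 80.8% with two. Under moderate selection, one or two losses bring the type I error of one comparison to about 5 to 6.5%. These error figures rest on assumed correlations of 0.3 to 0.5 and on a plain t-test rather than the SAP's mixed model.

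A reader might infer that the primary comparison is invalid as planned. The documents do not support that, since they give neither a refusal rate nor evidence of selection. What justifies a change is that the exposure is avoidable at little cost.

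**What to change.** In Protocol Section 8.3 and Table 2, move the IXRS allocation from the Run-In Period to Week 1 Day 1, after the pre-dose sample and the Day 1 pre-dose checks and immediately before the first injection. If supply needs an earlier assignment, keep it in Week -1 but withhold the cohort from patient and site until that moment. Loss before disclosure then cannot depend on knowledge of the cohort.

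In SAP Section 7.1.1, add a line for patients randomised but not dosed, by cohort and with the reason. The table already covers all randomised patients, so nothing else in it changes.

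The cost is protocol wording and an IXRS visit setting. Day 1 is already a required clinic visit, and the next dose is not until Day 15. Each site must hold enough vials on Day 1 for the largest planned dose: at an assumed 100 kg, 3.0 mg/kg × 100 kg = 300 mg, and 300 / 80 mg per vial = 3.75, so 4 vials. The sponsor must confirm that lot assignment and shipping allow this.
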